Randomization. Participants were allocated to the 2 study groups using simple balanced blocked randomization, stratified by facility. Randomization was implemented by use of allocation assignment concealed in a set of sequentially numbered opaque envelopes filled by research personnel not affiliated with the trial. Caregivers who enrolled with a patient participant were assigned to the same arm as the patient.

Intervention. Participants in the intervention arm received free access to a commercially available mindfulness program, HeadspaceTM (www.headspace.com), for 8 weeks. Headspace is a self-paced program that provides guided mindfulness meditation instructions via a website or mobile application (iOS and Android). Research staff emailed participants randomized to the intervention arm device-specific instructions for downloading the Headspace app and information about the program. Research staff checked in with participants over the phone a few days after emailing the instructions and provided support for setting up Headspace over the phone, if needed.

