Participants were asked to complete Headspace sessions on a daily basis during the 8-week intervention. They were encouraged to first complete the 30-day Foundation Course, which teaches users the basics of mindfulness meditation, then the cancer pack, which was designed specifically for individuals affected by cancer. They also had the option to choose other 10- to 30-day courses that are more condition- or situation-specific, such as "Anxiety," "Stress," "Acceptance," "Relationships," or "Sleep," or single meditation sessions. All Headspace courses teach mindfulness using various basic techniques, including breathing exercises, body scan (to mindfully pay attention to different parts of one's body—one of the most basic exercises in the MBSR program), noting (being aware of any emotions that may be arising at the moment), and visualization (visualizing images such as sun shining on the entire body). The length of the sessions can be set from 10 to 20 minutes. The length was initially set to 10 minutes for all participants. In addition to the daily, progressive audio instruction, there are short (1-2 minutes) lecture videos every several days designed to increase the understanding of mindfulness and to encourage its integration into daily life. Headspace can be set up to send reminders using push notifications, and study staff made phone calls if an intervention participant completed fewer than 3 Headspace sessions in a week.

Wait-list Control Arm. Participants randomized to the waitlist control arm received usual care and were asked not to start any stress reduction programs during the study period. On completion of the 8-week survey, the control participants were provided with a year's subscription to Headspace and instructions on downloading the app.

Outcome Measures

Retention. The retention rate was measured as the proportion of enrolled participants who completed the 8-week survey (the primary outcome time point).

Adherence. The Headspace program automatically collects adherence data, including date, time, length, and name of each session to which participants listened, identified by a study ID. Headspace transferred these adherence data to the researchers monthly during the study. Using these data, we calculated the proportion of days during the 8-week intervention period that each participant used the program for any amount of time.

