Mindfulness. The 24-item Five Facet Mindfulness Questionnaire–Short Form (FFMQ-SF) measures 5 factors representing elements of mindfulness: observing, describing, acting with awareness, nonjudging of inner experience, and nonreactivity to inner experience. Higher scores indicate greater mindfulness.

Post-Intervention Interview. We conducted phone interviews with participants after they completed the 8-week intervention period to obtain qualitative feedback regarding the study. Question topics included benefits of using Headspace, things they liked about Headspace or thought could be improved, suggestions for improving the experience of study participants, and experience being in the wait-list control arm.

Data Analyses

Data from patient participants and caregiver participants were analyzed separately. We described baseline distributions between arms. Retention rates were calculated by dividing the number of participants who completed the 8-week surveys by the number of randomized participants. We used the program usage data collected by Headspace to calculate intervention adherence rates—the percent of days within the 8-week intervention period that participants engaged in at least one Headspace session of any length.

To obtain preliminary efficacy results, we performed repeated measures analysis of variance tests comparing change in outcome measures between baseline and 8-week follow-up survey between intervention and control arms using all participants who completed both surveys. Cohen’s d effect size was calculated by taking the difference between group mean change scores and dividing by the pooled standard deviation. All analyses were intent-to-treat. As a pilot study, this randomized clinical trial was not adequately powered to detect statistically significant differences between groups. As such, standardized effect sizes were calculated to demonstrate effects and trends. Effect sizes of approximately 0.2, 0.5,

and 0.8 are generally considered small, medium, and large effects, respectively.

As a supplementary analysis, we conducted dose-response per-protocol analyses, repeating the analysis but stratifying intervention participants by level of adherence to the mindfulness intervention protocol (percent of days during intervention period used Headspace: <50% and $\geq 50\%$) and comparing with the control participants.

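### Does the switch from enrolled to randomized participants leave the retention denominator undefined?

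*Combined protocol and SAP*

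**What the plan says.** The retention denominator is named twice in the combined protocol and SAP.

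- **Outcome Measures, Retention:** "The retention rate was measured as the proportion of enrolled participants who completed the 8-week survey".
- **Data Analyses:** "Retention rates were calculated by dividing the number of participants who completed the 8-week surveys by the number of randomized participants".

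Four other statements bear on how the two words should be read.

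- **Randomization**, on the procedure: "Participants were allocated to the 2 study groups using simple balanced blocked randomization, stratified by facility". The same paragraph describes numbered opaque envelopes.
- **Randomization**, on caregivers: "Caregivers who enrolled with a patient participant were assigned to the same arm as the patient".
- **Intervention** and **Wait-list Control Arm** both use *randomized* for the members of an arm: "Research staff emailed participants randomized to the intervention arm device-specific instructions" and "Participants randomized to the waitlist control arm received usual care".
- **Data Analyses**, on populations: "Data from patient participants and caregiver participants were analyzed separately".

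The document gives no sample size, no enrolled, randomized or completing counts, no expected retention rate, and no retention threshold for moving to a larger trial.

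**The concern.** Retention is the first outcome measure listed, in a pilot that says it was not powered to detect differences between groups. Its denominator ought to be beyond doubt, yet the definition and the calculation use different words.

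Consent and the baseline survey are described as one online step, and allocation by envelope as another. In principle, people could be lost between the two. If some were, the randomized base would leave that loss out and give the higher rate, while a reader of the outcome definition might think it was included.

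Caregivers add a second doubt. Those who joined with a patient took the patient's arm and had no draw of their own, so a literal reader might ask whether they count as randomized. Because caregivers are analyzed separately, the answer would affect their rate directly.

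**Working it through.** **Inputs.** The two denominator statements come from Outcome Measures (Retention) and Data Analyses. There is no figure in the plan to reproduce. The sizes below rest on assumed values.

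**Step 1: how the two rates relate.** Let E be the number enrolled, A the number allocated, C the number completing the 8-week survey, and f = (E − A)/E the share enrolled but never allocated. Assume that every completer was allocated.

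- Enrolled-base rate: R_E = C/E
- Randomized-base rate: R_A = C/A = R_E/(1 − f)
- Difference: R_A − R_E = R_E × f/(1 − f)

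The randomized-base rate is equal or higher, never lower.

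**Step 2: assumed range.**

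| f (assumed) | R_E = 60% | R_E = 90% | Difference (points) |
|---|---|---|---|
| 0% | 60.0% | 90.0% | 0 |
| 2% | 60/0.98 = 61.2% | 90/0.98 = 91.8% | 1.2 to 1.8 |
| 5% | 60/0.95 = 63.2% | 90/0.95 = 94.7% | 3.2 to 4.7 |
| 10% | 60/0.90 = 66.7% | 90/0.90 = 100.0% | 6.7 to 10.0 |

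The last cell is a boundary case in which every allocated person completes.

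**Step 3: what the text says about f.** Nothing in it points to a value above zero. The Procedures section says that participants consented, and the Randomization paragraph says that participants were allocated. Both use the same unqualified noun, and neither makes an exception. The caregiver sentence uses *enrolled* and *assigned* together, but these are two acts, so two verbs are expected. For a denominator, what matters is whether the two groups contain different people. For caregivers who joined with a patient, that sentence says they do not. This does not prove f = 0, but it makes *enrolled* most naturally a loose synonym.

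**Step 4: whether co-enrolled caregivers count as randomized.** The Intervention and Wait-list Control Arm paragraphs describe what each arm received, and both speak of those randomized to the arm. If that excluded caregivers assigned with a patient, the document would not say what those caregivers received at all. The workable reading is that *randomized* covers everyone placed in an arm.

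**Step 5: which statement governs.** Data Analyses gives an explicit numerator and denominator. Its denominator has a plain meaning through the described allocation procedure. Only *enrolled* is undefined, and the calculation does not use that word.

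**The case for a change.** The best case for acting is that no sentence equates the two words, that consent and allocation are described as separate procedures, and that a retention figure should not hide early loss. A single word in the outcome definition would remove the doubt at almost no cost, and counts of people consented, allocated and completing would show any loss.

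The first part stands as a matter of wording: the terms differ, and the document never says that everyone enrolled was allocated.

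The rest does not lead to a change. The tidier definition would be all participants allocated to an arm, which is what Data Analyses already uses, so the calculated rate would stay the same. Loss before allocation can fairly be treated as a recruitment matter, and leaving it out of retention is a legitimate choice. Flow counts belong in the results report, and this is a methods text without results. Nor could consent counts be split by arm for the people at issue, since anyone never allocated has no arm.

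**Conclusion.** The concern identifies a real slip in terminology but not a defect in the analysis. The plan's own formula, completers over randomized participants, is explicit and sound, and the other sections give enough to apply it to patients and to caregivers separately.

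The effect on the rate is zero if everyone enrolled was allocated, which is the natural reading. The non-zero differences rest wholly on assumed values of f and on the assumption that all completers were allocated. Even then, no stated criterion turns on them. Matching the word in the outcome definition to the one in the analysis section would be harmless tidying, but it would not alter what is computed or concluded. No change to the plan follows.

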**POEM (Practice Of Embracing Each Moment) STUDY
NCT03078608**

04/19/2019

Methods

Setting

The POEM (Practice Of Embracing each Moment) study was conducted within Kaiser Permanente Northern California (KPNC), an integrated health care delivery system that provides comprehensive health care to a large, diverse community-based population of over 4.1 million individuals. KPNC provides coverage for approximately 31% of the northern California population, and its membership is similar demographically, ethnically, and socioeconomically to the area's overall population. The only exception is with regard to income; KPNC members underrepresent the very poor and the very wealthy. Participants for the POEM study were recruited from 7 KPNC oncology clinics in the San Francisco Bay Area.

Participants

We included patients with a diagnosis of cancer who were currently receiving or had received chemotherapy, targeted therapies, or immunotherapy in the prior 6 months. The inclusion criteria for both patients and caregivers included age ≥ 18 years; owning a smartphone, tablet, or computer with internet access; and understanding English. Primary informal caregivers of the patients were also eligible and invited to participate. We excluded persons who regularly meditated or prayed at least 3 times per week, were currently participating in another type of stress reduction program, were severely hearing impaired, or had severe mental illness.

Procedures

This 2-arm randomized controlled pilot trial was conducted between October 2017 and November 2018. Participants completed an online informed consent form, and study protocols and procedures were approved by the KPNC Institutional Review Board. The study was registered on ClinicalTrials.gov (NCT03078608).

Recruitment. Patients were recruited using several strategies, including clinic referrals from oncologists, oncology social workers, and nurses; brochures at each clinic; and invitation emails, followed up with phone calls. Eligible patients were identified using the KPNC electronic health record. Caregivers were recruited by patient participant referral. Patients could participate with or without caregiver participation, and caregivers could also participate without an enrolled patient. Participants who completed the study received a \$40 gift card and a year's subscription to the mindfulness program used for this trial.

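### Efficacy tests and Cohen's d use unadjusted change scores, which usually costs precision and lets a chance baseline difference move the effect sizes

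*Combined protocol and SAP*

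**What the plan says.** All references are to the combined protocol and SAP.

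- **Test (Data Analyses).** For efficacy, "we performed repeated measures analysis of variance tests comparing change in outcome measures between baseline and 8-week follow-up survey", compared between arms among people who completed both surveys.
- **Effect size (Data Analyses).** For Cohen's d, the "effect size was calculated by taking the difference between group mean change scores and dividing by the pooled standard deviation". The text does not say whether the pooled SD is that of change or of raw scores.
- **Role of the effect size (Data Analyses).** The section concedes that the pilot lacks power for significance tests between arms and continues: "As such, standardized effect sizes were calculated to demonstrate effects and trends". Values near 0.2, 0.5 and 0.8 are its benchmarks for small, medium and large.
- **Time points (Participant-Reported Measures).** There are two surveys, one at consent and one at 8 weeks.
- **Subsets (Data Analyses).** "Data from patient participants and caregiver participants were analyzed separately".
- **Allocation (Randomization).** "simple balanced blocked randomization, stratified by facility". Nothing balances the arms on outcome scores.

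Baseline distributions are described by arm, but no baseline score, facility term or other covariate is named in any model. The supplementary analysis by adherence level repeats the same method.

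**The concern.** A change score subtracts the whole baseline value, as if a participant who starts one point higher would be expected to finish one point higher. Symptom scores usually regress towards the mean, so the true slope is below 1 and subtraction over-corrects. Suppose the intervention arm happens to start more distressed. Its scores will then tend to fall further with no treatment effect, and the change-score difference will look like benefit. If it starts less distressed, a real benefit is understated.

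The efficacy reading rests on standardised differences in mean change, which are the quantities that such an imbalance moves. Two features add to the exposure. Patients and caregivers are analysed apart, so each comparison is smaller than the trial. Restriction to completers also means that the balance created by randomisation is not guaranteed in the analysed set.

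**Working it through.** **Inputs.** From the documents: two time points, balanced allocation (taken as 1:1), no baseline covariate, and benchmarks of 0.2, 0.5 and 0.8. The plan states no sample size, SD, correlation or power figure, so there is nothing of its own to reproduce. Assumed: correlation r between baseline and 8 weeks of 0.3 to 0.8; SD ratio k (8 weeks over baseline) of 1 unless stated; 15 to 50 participants per arm.

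**Step 1: the planned test is a change-score t-test.** With two time points, the arm-by-time F equals the squared t on change scores. On one simulated data set with 30 per arm, both were 3.914.

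**Step 2: precision.** Per-participant variance, in units of baseline variance:

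- change score: 1 + k² − 2rk
- ANCOVA: k²(1 − r²)

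For k = 1 these are 2(1 − r) and 1 − r², with ratio (1 + r)/2.

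| r | Change | ANCOVA | Ratio | Equivalent extra participants (1/ratio − 1) | CI narrower by (1 − √ratio) |
|---|---|---|---|---|---|
| 0.3 | 1.40 | 0.91 | 0.65 | 54% | 19% |
| 0.5 | 1.00 | 0.75 | 0.75 | 33% | 13% |
| 0.7 | 0.60 | 0.51 | 0.85 | 18% | 8% |
| 0.8 | 0.40 | 0.36 | 0.90 | 11% | 5% |

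Estimating the slope costs a little in small samples. Multiplying by (N − 3)/(N − 4), with N the total in both arms, gives 0.68, 0.78, 0.88, 0.93 at 15 per arm (factor 27/26) and 0.66, 0.76, 0.86, 0.91 at 40 per arm (factor 77/76). Simulation agreed to within about 0.01.

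The gain depends on the slope rk. At r = 0.8 and k = 1.25 the slope is 1 and both variances are 0.5625. The ratio is then 1.00, or 1.04 at 15 per arm and 1.01 at 40 after the slope is estimated. At r = 0.5 and k = 0.8 the ratio is 0.48/0.84 = 0.57.

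**Step 3: shift given a chance baseline difference D (intervention minus control), k = 1.** The change-score estimate moves by −(1 − r)D. For D = 0.3 baseline SD:

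| r | Shift in baseline SD: 0.3(1 − r) | Shift in change SD: divide by √(2(1 − r)) |
|---|---|---|
| 0.3 | 0.21 | 0.18 |
| 0.5 | 0.15 | 0.15 |
| 0.7 | 0.09 | 0.12 |
| 0.8 | 0.06 | 0.09 |

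In 40,000 simulated trials with no arm effect and 15 per arm, the mean change-score estimate was within 0.003 of zero. Its regression on D had slopes of −0.70, −0.50, −0.30 and −0.20; the ANCOVA slope was within 0.01 of zero.

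**Step 4: how often D is that large.** The SD of D is √(2/n) for n per arm: 0.365 at 15 and 0.224 at 40. The chance of |D| ≥ 0.3 on a given outcome is 0.41, 0.29, 0.18 and 0.13 at 15, 25, 40 and 50 per arm.

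**Step 5: facility.** If the 7 recruiting clinics are the strata, facility uses 6 degrees of freedom. With f the share of residual variance it explains, CI width changes by √(1 − f) × t(N − 9)/t(N − 3). That is 1.014 at N = 30 with f = 0, and 0.950 at N = 90 with f = 0.10.

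**The case against.** The strongest reply is that this is a preference about efficiency and not an error. Change-score analysis is conventional and unbiased over randomisation. The precision loss and the conditional shift are also one mechanism: 2(1 − r) = (1 − r²) + (1 − r)², and the last term is the variance that chance baseline differences contribute. An unadjusted confidence interval already allows for it. At 15 per arm, the shifts for D = 0.3 SD are only 0.49, 0.41, 0.32 and 0.26 of the change-score standard error. All of this is right, and the two effects must not be added together. It does not defend the method: the observed baseline difference is known, and the analysis can remove its effect.

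Three further points stand as limits.

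- The size rests wholly on assumed inputs. If d is scaled by the SD of change, the shifts for D = 0.3 SD all fall below 0.2.
- Adjustment does not rescue power. At an assumed 25 per arm and a true difference of 0.5 raw SD (two-sided 5%), power is 0.32 against 0.46, 0.42 against 0.53 and 0.63 against 0.70 at r = 0.3, 0.5 and 0.7, for change score against ANCOVA.
- If dropout differs by arm, neither analysis of completers is guaranteed unbiased.

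Facility matters little. Stable differences in level between facilities cancel in change scores, and the documents do not say that the strata are the 7 clinics.

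**Conclusion.** The concern holds. The efficacy tests and Cohen's d are unadjusted change-score comparisons, and a baseline score already in hand goes unused. For correlations of 0.3 to 0.8 with equal SDs, ANCOVA would cut variance by 35% down to 10% in large samples, and slightly less in small ones. It would also remove, on average, a conditional shift of 0.21 down to 0.06 baseline SD for each 0.3 SD of imbalance. If the true slope is 1 there is no gain and a slight loss.

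That the plan does not adjust is certain; how much this cost the trial cannot be computed from the documents. The change is worth making because the pilot's efficacy reading rests on these effect sizes. It does not invalidate the planned tests, and it leaves the retention and adherence results untouched.

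**What to change.** For each outcome, separately in patients and caregivers, regress the 8-week score on arm and that outcome's own baseline score. Report the adjusted mean difference with its 95% CI, and obtain the effect size by dividing it by a named SD, for example the pooled baseline SD. Naming the SD matters: dividing the same raw difference by the change SD instead would multiply d by 0.85, 1.00, 1.29 and 1.58 at r = 0.3, 0.5, 0.7 and 0.8.

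Keep the unadjusted change analysis beside it. The text reports that "This 2-arm randomized controlled pilot trial was conducted between October 2017 and November 2018", so an adjusted analysis added after the original one must be labelled post hoc.

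Secondarily, for consistency with the stratified allocation, add facility with sparse facilities merged, or use it only as a sensitivity analysis in the smaller caregiver sample.

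No new data are needed, since baseline scores and facility are already recorded. The cost is a reanalysis, one degree of freedom for the baseline score, up to 6 for facility, and a slight loss of precision if the slope is near 1 or facility explains nothing.

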Participant-Reported Measures. We collected outcome data using self-administered online surveys using DatStat software (DatStat Ilume, version 6.1.18.19, Seattle, WA) at the time of consent (baseline survey) and immediately post-intervention (8-week survey) using validated questionnaires as follows.

Distress. The NCCN Distress Thermometer was used to assess current distress level. Respondents were asked to rate their level of distress during the past week by choosing a number, with 0 indicating no distress and 10 extreme distress.

Anxiety and depression. We used the 14-item Hospital Anxiety and Depression Scale (HADS) to assess anxiety and depression. Higher scores indicate greater anxiety and depression.

Pain. The PROMIS Pain Intensity numeric rating scale asks participants to rate average pain level in the past 7 days on a scale of 0 (“no pain”) to 10 (“worst imaginable pain”). The 8-item PROMIS Pain Interference scale assesses extent to which pain interfered with functional activities during the past 7 days. Higher scores indicate more interference due to pain.

Sleep quality. The 8-item PROMIS Sleep Disturbance scale assesses sleep disturbance during the past 7 days. A higher summary score indicates worse sleep disturbance.

Quality of life. We used the 27-item Functional Assessment of Cancer Therapy General Scale (FACT-G) to assess QoL in patients. FACT-G asks respondents to rate their QoL in 4 domains (physical, social/family, emotional, and functional well-being). Caregiver QoL was determined using the Caregiver Quality of Life Index–Cancer (CQOLC) scale. The CQOLC gauges the daily and overall impact caregiving has on respondents’ QoL. Higher scores indicate better QoL on both scales.

Fatigue. The 9-item Brief Fatigue Inventory assesses the severity and impact of fatigue on various aspects of life in the past 24 hours. Higher scores indicate greater fatigue.

Posttraumatic growth. The 21-item Posttraumatic Growth Inventory (PTGI) assesses 5 factors of posttraumatic growth, positive change experienced because of a traumatic event or crisis—relating to others, new possibilities, personal strength, spiritual change, and appreciation of life. Respondents are asked to rate to what extent they have seen the listed changes as a result as a crisis in their lives. We modified the wording to ask about changes as a result of their (patients) or their loved one’s (caregivers) cancer diagnosis. Higher scores indicate greater post-traumatic growth.

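### The efficacy comparison is labelled intent-to-treat but analyses only participants with both surveys, and no sensitivity analysis covers randomised participants without the 8-week survey

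*Combined protocol and SAP*

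**What the plan says.** All references are to the combined protocol and SAP.

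- **Data Analyses, efficacy method.** The text says "we performed repeated measures analysis of variance tests comparing change in outcome measures between baseline and 8-week follow-up survey between intervention and control arms", and limits this to a set formed by "using all participants who completed both surveys". Cohen's d is the between-arm difference in mean change, obtained by "dividing by the pooled standard deviation".
- **Data Analyses, label.** The same paragraph then states "All analyses were intent-to-treat". It adds that the pilot lacks power, so standardised effect sizes are used to show effects and trends.
- **Participant-Reported Measures.** There are two surveys: one at consent and one straight after the 8-week period. No intermediate survey is described.
- **Retention.** Under Outcome Measures: "The retention rate was measured as the proportion of enrolled participants who completed the 8-week survey". Under Data Analyses, the rate is found by "dividing the number of participants who completed the 8-week surveys by the number of randomized participants". The plan therefore separates those randomised from those who completed.
- **Supplementary analysis.** The one further efficacy analysis repeats the comparison with intervention participants split at 50% of days of app use. It does not address missing 8-week surveys.
- **Not described.** There is no imputation, no model that includes all randomised participants, no comparison of completers with non-completers, and no other missing-data sensitivity analysis.

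**The concern.** The label and the analysed set do not match in the usual sense of intent-to-treat, which keeps everyone randomised in the comparison. Baseline is collected at consent, so in practice the restriction acts on completing the 8-week survey, which happens after randomisation. Randomisation protects a comparison of everyone assigned. It does not by itself protect a comparison of those who stayed.

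What is at stake is how the effect sizes are read. They are the pilot's efficacy output, and the label could lead a reader to think they cover everyone randomised. If dropout were related to how participants felt at the start or to how they changed, the completer estimate could be off in either direction, and nothing described in the plan would show it.

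**Working it through.** **Step 1: who enters the comparison.** With two time points, the arm-by-time test in a repeated measures ANOVA compares mean change between arms, and d is built on the same change scores. Both need an 8-week value. A randomised participant without one adds nothing to either. That the completers are compared by assigned arm is an inference from the label and from the comparison of intervention with control. The text does not say it in those words, but it is the natural reading.

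**Step 2: is there a figure to reproduce?** No. The documents give no sample size, retention rate, SD or pre-post correlation. Everything below is an assumption-only illustration of direction and rough size.

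**Step 3: assumptions.** Scores are oriented so that higher is better, with SD 1 at both times and no true effect. Retention is 70% (app) and 90% (control). Pre-post correlation ρ is 0.5 to 0.7. The probit slope b of staying on the dropout variable is 0.3 to 0.5 per baseline SD. For a dropout variable with variance v and retention p, completers' mean is shifted by

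shift = b·v/√(1 + b²v) × φ(z_p)/p,

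where φ(z_p)/p is 0.3477/0.70 = 0.497 at 70% and 0.1755/0.90 = 0.195 at 90%. Results are in baseline SD, because the plan does not say which pooled SD divides d.

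**Step 4: those with worse change drop out.** Here v = 2(1 − ρ), which is 1.0 at ρ = 0.5 and 0.6 at ρ = 0.7.

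- Upper end (ρ = 0.5, b = 0.5): 0.5/√1.25 = 0.447. App shift 0.447 × 0.497 = 0.222; control shift 0.447 × 0.195 = 0.087.
- Lower end (ρ = 0.7, b = 0.3): 0.18/√1.054 = 0.175. App shift 0.175 × 0.497 = 0.087; control shift 0.175 × 0.195 = 0.034.

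| Outcome-related dropout | Bias in favour of the app |
|---|---|
| App arm only | 0.087 to 0.222 |
| Same mechanism in both arms, 70% vs 90% | 0.087 − 0.034 = 0.053, to 0.222 − 0.087 = 0.135 |
| Same mechanism in both arms, equal retention | 0 |

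**Step 5: app participants with worse baseline drop out.** Now v = 1. Completers' baseline mean rises by the shift s, but their 8-week mean rises only by ρs, so their change moves by −(1 − ρ)s, against the app.

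- Upper end (ρ = 0.5, b = 0.5): 0.5 × 0.222 = 0.111.
- Lower end (ρ = 0.7, b = 0.3): s = 0.3/√1.09 × 0.497 = 0.143, and 0.3 × 0.143 = 0.043.

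This bias needs both the exclusion of non-completers and the use of unadjusted change. With nobody missing, s = 0 and the change score is unbiased. With baseline adjustment, the shift is removed.

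**Step 6: check by simulation.** I simulated 8,000 trials per scenario with 50 per arm (assumed), ρ of 0.5 and 0.7 and b of 0.3 and 0.5. The change-score results agreed with the closed forms. Completer ANCOVA (8-week score on baseline and arm) was within 0.01 of 0 under baseline-related dropout. Under outcome-related dropout in the app arm only, it was still off by about 0.07 to 0.17.

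**Step 7: compare with chance error.** With 35 and 45 completers, the sampling SD of the difference in mean change is √[2(1 − ρ)(1/35 + 1/45)], which is 0.225 at ρ = 0.5 and 0.175 at ρ = 0.7. The largest bias, 0.222, about equals it. The others are smaller, most of them clearly so.

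**The case against.** The strongest reply is that the label misleads little. The analysed set is stated in the same paragraph, just before it. The next paragraph contrasts it with a per-protocol analysis by app use, so intent-to-treat most naturally means as assigned, whatever the level of use. Efficacy is called preliminary and the trial is declared underpowered. All of this stands, and it limits the severity. It does not restore the omitted participants, and no other analysis covers them.

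Three stronger readings are tempting, and the documents support none of them.

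- *That dropout differed by arm.* No dropout is reported. The sentence beginning "Participants who completed the study received", under Recruitment, offers the completion reward without restricting it by arm. The arms did have different experiences (daily sessions and staff calls for low use, against usual care). That is a reason to look at completion by arm, not evidence that it differed.
- *That the effect sizes are inflated in favour of the app.* The direction is unknown. Outcome-related and baseline-related dropout push opposite ways when it is the worse-off app participants who leave, and the two can partly cancel. If non-completers did better than completers, the signs reverse.
- *That retention was not shown by arm.* The text is a methods section in the past tense with no results. Its silence on an arm split does not show that the split went unreported. Separate analysis of patients and caregivers is already stated.

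**Conclusion.** The point holds as a minor to moderate one. The efficacy comparison is a completer analysis by assigned arm under an intent-to-treat label, with no sensitivity analysis for randomised participants who lack the 8-week survey. It does not invalidate the pilot.

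No bias can be sized from the documents. The illustrated range, from about 0.22 baseline SD in favour of the app to about 0.11 against it, with 0 when the same mechanism and equal retention hold in both arms, rests wholly on the assumed retention, correlation and dropout slopes. Only the top of that range reaches what the plan calls a small effect (0.2). The mislabelling itself is read directly from the text and needs none of these assumptions.

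**What to change.** 1. For the efficacy comparison, replace "All analyses were intent-to-treat" with *completers analysed in their assigned arm*.
2. Show 8-week survey completion by arm (completed / randomised) beside the effect sizes, within patients and within caregivers.
3. Report a baseline-adjusted ANCOVA estimate (8-week score on baseline and arm) beside the change-score result, disclosed as post hoc. It removes bias from baseline-related dropout, but not from outcome-related dropout.
4. Optional: a shift check, disclosed as post hoc and in a stated SD, run in both directions and in both arms. The adjusted effect is the completer effect − (m_app × g_app − m_control × g_control), where m is the share missing and g is how much worse non-completers did than completers (negative if better). For example, take a completer effect of 0.30 with 30% and 10% missing. It becomes 0.30 − (0.15 − 0.05) = 0.20 if non-completers were 0.5 SD worse in both arms, 0.15 if worse in the app arm only, and 0.45 if 0.5 SD better in the app arm only.

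The cost is one reworded sentence, one split of a rate already planned, and a little extra analysis of data already collected. Items 3 and 4 must be marked post hoc because the trial ended in November 2018. No new participants or visits are needed.
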